7.2 Primary Endpoint

7.2.1 Analysis of the primary endpoint

The primary endpoint is the total nasal symptoms score (TNSS) measured at 0, 5, 15, 30 and 60 minutes (Early phase response (EPR)) following grass pollen nasal allergen challenge at 12 months (Appendix 6).

The endpoints will compare the following groups:

- SLIT versus SLIT Placebo
- SLIT versus SLIT Placebo versus non-atopic controls

This study requires the analysis of longitudinal data since the outcome of interest is measured over a period of time. Longitudinal analysis allows estimating the marginal effect of the predictors of interest such as Age, Gender, Skin Prick test, specific IgE, baseline visual analogue scale and compliance as well as the comparison between the intervention and control group. Longitudinal analysis also allows the assessment of changes over time. One of the comparisons of interest is the difference between the intervention and control groups at baseline, 6 months and 12 months. The other relevant comparison is the average EPR at 12 months with baseline for both groups. Longitudinal data require special statistical methods because observations made on each subject are correlated. This correlation must be taken into account to draw valid statistical inferences. Some of the approaches that model the correlation structure in longitudinal data are Models for the Mean response and Random coefficient models.

Also, before the main analysis exploratory analysis will be carried out: box plots, scatter plots, cross-tabs, frequency tables and summary statistics.

This will be analysed using the ITT sample and for the PP analysis population.

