6.1 Primary endpoint

The area under the curve (AUC) of the early phase response (total nasal symptom score, TNSS, 0-60 minutes) following grass pollen nasal allergen challenge in active versus placebo-treated atopic participants at 12 months.

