6.3.2 Inclusion Criteria

Atopic participants:

1. Adults age 18 to 65 years.
2. A clinical history of grass pollen-induced allergic rhinoconjunctivitis for at least 2 years with peak symptoms in mid-May to mid-July.
3. A clinical history of moderate to severe rhinoconjunctivitis symptoms with or without mild seasonal asthma interfering with usual daily activities or with sleep.
4. A clinical history of rhinoconjunctivitis with or without mild seasonal asthma that remains troublesome despite treatment with either antihistamines or nasal corticosteroids during the grass pollen season.
5. Positive skin prick test response, defined as wheal diameter ≥ 3 mm, to timothy grass pollen.
6. Positive specific IgE, defined as IgE immunoCAP ≥ 0.7 ISU, against timothy grass pollen.
7. For women of childbearing age, a negative urine pregnancy test at the time of screening and willingness to use an effective form of contraception for the duration of involvement in the study.
8. The ability to give informed consent and comply with study procedures.
9. A positive grass pollen nasal allergen challenge test at screening as defined by a total nasal symptom score (TNSS) of at least 7/12 after 5 minutes with an allergen dose of 5,000 BU/ml (**Appendix 6**) (see also section 6.5.7).

Healthy, non-atopic participants:

1. Adults age 18 to 65 years.
2. Negative skin prick test response to timothy grass pollen and panel of aeroallergens.
3. Negative specific IgE, defined as IgE immunoCAP < 0.35 ISU, against timothy grass pollen.
4. For women of childbearing age, a negative urine pregnancy test at the time of screening and willingness to use an effective form of contraception for the duration of involvement in the study.
5. The ability to give informed consent and comply with study procedures.

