6.8.3.1. Analysis of Primary Endpoint

The primary endpoint is defined in section 6.1 and will be analysed using the ITT sample. The analysis of the primary endpoint will compare the mean EPR to nasal challenge recorded by the AUC of the TNSS during the first 60 minutes after the nasal challenge, at 12 months of therapy. Comparison between active and placebo groups will be assessed using ANOVA at the 0.05 level of significance.

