5. STUDY SUBJECTS

5.1 Demographic and Other Baseline Characteristics

Summary descriptive statistics for baseline and demographic characteristics will be reported for the randomized atopic and non- atopic sample.

Demographic data will include and data will be adjusted for age, gender, Skin Prick test (screening), specific IgE (screening) and compliance.

Furthermore the following characteristics will be used for descriptive statistics only: baseline visual analogue scale (How has your Hayfever been overall in the previous season? (Appendix 2 from Protocol), Polisensitisation (this will be defined as a positive skin prick test during screening apart from skin prick test to timothy grass and the positive control (Yes/No), seasonal asthma, this information will be taken from the medical and allergy history from the participant (Yes/No), total IgE, BMI, ethnicity.

These data will be presented in the following manner:

- Continuous data (e.g., age) will be summarized descriptively by mean, SD, median, min, and max.
- Categorical data (e.g., sex and ethnicity) will be presented as frequencies and percentages.

Demographic and baseline characteristic data will also be presented in data listings by study group (atopic (placebo and active group) and non-atopic).

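### The SAP lists a three-group comparison with non-atopic controls under the primary endpoint, without order or role, and applies a model that cannot validly include those controls

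*SAP*

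**What the plan says.** Protocol 6.1 defines the primary endpoint as the TNSS AUC over 0-60 minutes after nasal challenge, "in active versus placebo-treated atopic participants at 12 months". Protocol 6.8.3.1 gives one test: "Comparison between active and placebo groups will be assessed using ANOVA at the 0.05 level of significance". Protocol 6.8.1 sizes two groups for this endpoint.

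SAP 7.2.1 lists two comparisons for the primary endpoint: SLIT versus placebo, and "SLIT versus SLIT Placebo versus non-atopic controls". It gives no order, contrast or role for either. The method is a longitudinal model with "predictors of interest such as Age, Gender, Skin Prick test, specific IgE, baseline visual analogue scale and compliance", run in the ITT and PP samples, and the time points of interest are baseline, 6 and 12 months. SAP 5.1 states the adjustment more firmly: "data will be adjusted for age, gender, Skin Prick test (screening), specific IgE (screening) and compliance". There the baseline VAS is kept for description only.

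On eligibility, Protocol 6.3.2 requires of atopic participants "Positive skin prick test response, defined as wheal diameter ≥ 3 mm, to timothy grass pollen" and specific IgE of at least 0.7 ISU. It requires of controls "Negative skin prick test response to timothy grass pollen and panel of aeroallergens" and "Negative specific IgE, defined as IgE immunoCAP < 0.35 ISU, against timothy grass pollen".

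SAP 7.3 (secondary endpoints) and 7.3.2 (mechanistic assessments) repeat the three-group comparison and refer back to the primary method.

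**The concern.** There are two separate problems.

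- **Role.** The SAP puts a second comparison at the level of the primary endpoint, which the protocol did not plan there, and does not rank it. The statement in SAP 7.3 that p-values are supportive and unadjusted covers secondary endpoints only. A reader of the results could not tell from the SAP which primary-level p-value answers the trial's question.
- **Model.** The adjustment set and analysis samples were written for randomised, tablet-taking, allergic participants. Applied to controls, they either remove the controls or make their adjusted mean an extrapolation.

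At stake is the reading of the primary result and the usefulness of every comparison with controls, because the secondary and mechanistic sections inherit the same method.

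**Working it through.** **1. Can the controls enter the model as written?**

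| Element of the SAP model | Status of the controls | Source |
|---|---|---|
| ITT sample (all randomised); PP (a subset of ITT) | Not randomised, so in neither | SAP 3; Protocol 6.3.8 |
| Challenge at baseline, 6 and 12 months | One challenge, at 12 months; none at screening | SAP 7.2.1; Protocol 6 and 6.5.14 |
| Compliance (count of study tablets) | No tablets, so no value | SAP 6.2; Protocol 6.3.8 |
| Skin prick test to timothy grass | Negative, against wheal ≥ 3 mm | Protocol 6.3.2 |
| Specific IgE | < 0.35 ISU, against ≥ 0.7 ISU | Protocol 6.3.2 |
| Baseline VAS | Collected at control screening | Protocol 6.5.14 |
| Age, gender | Age 18 to 65 in both lists; no restriction by gender | Protocol 6.3.2 |

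Three of the six named covariates fail: compliance, skin prick test and specific IgE. With compliance in the model, a complete-case fit goes from 22 + 22 + 20 = 64 to 44 participants, and the three-group comparison becomes the two-group one.

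**2. What if compliance is dropped and the controls are kept?** Simulated data obeying the eligibility cut-offs were fitted with group, log10 specific IgE and skin prick wheal. The distributions are assumed: atopic IgE log-normal, cut at 0.7; control IgE uniform below 0.35; atopic wheal mean 8 mm, SD 2.5, cut at 3; control wheal 0. Adding the two covariates inflates the variance of the control term about 6.9-fold, so its SE rises by √6.9 ≈ 2.6. The active-versus-placebo SE rises by a factor of only about 1.02.

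**3. The plan's own figures.** Protocol 6.8.1 gives mean 4.63 and SD 1.65. With n per group = 2 × ((1.960 + 0.842) × SD / δ)², two-sided 0.05 and 80% power:

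- 30% reduction, δ = 0.30 × 4.63 = 1.389: n = 22.2, rounded up to 23 (stated 22; power at 22 is 79.7%, or 77.9% by the t-test).
- 40% reduction, δ = 0.40 × 4.63 = 1.852: n = 12.5, rounded up to 13 (stated 13).

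The stated sizes are reproduced within one participant, for two groups. The point does not depend on them; they supply the mean and SD for the next step.

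**4. If the three groups were tested together, unadjusted, with no AIT effect.** Take both atopic means as 4.63, a common SD of 1.65, and n = 22/22/20. The noncentrality is λ = (44 × 20 / 64) × (4.63 − c)² / 1.65² = 13.75 × (4.63 − c)² / 2.7225, where c is the control mean. The F critical value with 2 and 61 df is 3.15. The documents give no c, so a range is shown. The last column divides λ by 6.9, the inflation from step 2, and assumes that the covariates have no effect of their own.

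| Assumed control mean c | λ | Rejection, unadjusted | Rejection, λ / 6.9 |
|---|---|---|---|
| 0.5 | 86.1 | > 99.9% | 88% |
| 1 | 66.6 | > 99.9% | 78% |
| 2 | 34.9 | > 99.9% | 49% |
| 3 | 13.4 | 90% | 21% |
| 3.5 | 6.4 | 59% | 12% |
| 4 | 2.0 | 22% | 7% |

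With equal atopic means, rejections above the nominal 5% come from the gap between controls and atopic participants, not from treatment.

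**The case against.** The strongest reply is that the efficacy comparison is intact, and it is. SLIT versus placebo is listed first and on its own. The SAP's time-point comparisons are framed for the intervention and control arms, and by its own sample definitions the non-atopic group is outside the primary population. A reader might infer that the three-group listing stops the trial from informing on AIT efficacy. The documents do not support that: the randomised contrast remains, and its precision barely changes even if controls share the model.

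A reader might also infer that the SAP commits to an omnibus test that is almost certain to reject. It says only that groups will be compared and names no F-test or decision rule. The high rejection rates belong to an unadjusted test at assumed control means, and they fall steeply as that mean nears 4.63 or once the separated covariates are included. Nor can all the harms occur in one fit: if complete-case fitting removes the controls, there is no three-group p-value to misread.

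The covariate problem is also not general. Age and gender can overlap, and the VAS is recorded in controls.

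Finally, controls have a planned role. Protocol section 6 has them undergo the clinical surrogate assessments as a reference at 12 months, and Protocol 6.2.1 (endpoints 2 and 3) plans comparisons with them. Comparing with controls is therefore legitimate; the unranked listing and the model applied are not.

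**Conclusion.** The point holds in limited form. SAP 7.2.1 attaches to the primary endpoint a comparison that the protocol does not plan there, gives it no rank, and specifies a model that cannot validly include the controls. This goes beyond missing detail, because the adjustment rule as stated gives either no control comparison (all 20 dropped) or one resting on extrapolation across a gap that eligibility creates. These findings follow from the documents and need no assumed figures.

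Two sizes do rest on assumptions. The 6.9-fold inflation depends on the simulated covariate distributions. The omnibus rejection rates depend on an assumed control mean and on a test that the SAP does not name; they show only that such a result, if produced, would not be evidence about AIT. Confidence is high on the structural fault and low on any single rejection figure. It should be corrected, but it does not threaten the randomised comparison.

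**What to change.** Change the SAP wording as follows.

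1. In 7.2.1, name SLIT versus placebo in the ITT sample as the sole primary comparison, with PP as supportive.
2. Move the controls to a separate paragraph: 12 months only, outside ITT and PP, labelled non-randomised, and reported as pairwise estimates (SLIT versus controls, placebo versus controls) with confidence intervals.
3. Leave skin prick test, specific IgE and compliance out of those estimates. Leave out baseline VAS too, since SAP 5.1 makes it descriptive only.
4. Apply the same rule wherever SAP 7.3 and 7.3.2 compare with controls. SAP 7.3.2 already limits controls to the 12-month time point, so its wording can serve as the model. In 7.3, remove controls from items that need a change from baseline, which controls cannot supply.

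The cost is a few sentences in the SAP, with no new data, visits or participants.

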7.3 Secondary Endpoints

This study is not designed or powered to perform hypothesis testing on secondary endpoints. All secondary analyses will be treated as supportive. P-values will be presented for the secondary endpoints but will not be adjusted for multiplicity. The endpoints listed below will compare the following groups using the same statistical methodology as described for the primary endpoint.

- SLIT versus SLIT Placebo
- SLIT versus SLIT Placebo versus non-atopic controls

1. Peak nasal inspiratory flow (PNIF) measured at 0, 5, 15, 30 and 60 minutes (EPR) following grass pollen nasal allergen challenge at baseline and at 12 months.

2. Mean LPR to intradermal testing recorded as the mean diameter of the swelling (longest diameter plus perpendicular diameter, exclude pseudopods) measured at the specified time points - after 8 hours of allergen challenge respectively - at baseline and after 12 months of treatment.
3. Mean EPR to intradermal testing recorded as the mean diameter of the swelling measured at the specified time points - after 15 minutes of allergen challenge respectively - at baseline and after 12 months of treatment.
4. Global seasonal visual analogue score 1 (Appendix 1 of the protocol) after the pollen season 2014 (single measurement and delta (comparing baseline with after pollen season time point))
5. Global Evaluation score 2 (retrospective individual global evaluation) (Appendix 2 of the protocol) after the pollen season 2014 (single measurement only).

7.3.1 Exploratory Endpoints

The endpoints listed below will compare the following groups using the same statistical methodology as described for the primary endpoint.

- SLIT versus SLIT Placebo

1. Symptoms and medication scores (AUC) scores (Appendix 5 of the protocol) will be self-assessed weekly during the pollen season from May 2014 until end of July 2014 by the atopic participants. The symptom score will encompass nose and eye symptoms recorded on a scale from 0 to 3 (with a score of 0 indicating no symptoms, 1, 2 and 3 indicating mild, moderate and severe symptoms respectively). The maximum score is therefore 18. All possible rescue medication will be provided to each participant before the Hayfever season in May. They will be asked to use the treatment on an as required basis only, starting with the antihistamines (tablets and/or eye drops) and if this does not suffice adding treatment with nasal spray. In case this still does not relieve their symptoms they will be advised to contact the trial team to start Prednisolone 30 mg 3-5 days. Medication use will be recorded in weekly questionnaires by participants and a medication score will be calculated: desloratadine, 5 mg, up to 1 tablet daily and/or olopatadine eye drops, 1.0 mg/mL, up to 1 drop per eye twice daily (1 point per day); fluticasone nasal spray, 50 mcg per spray, up to 2 sprays per nostril once daily (2 points per day); and prednisone, 5 mg per tablet, up to 6 tablets per day (3 points per day). The maximum daily medication score will therefore be 3. The maximum weekly score will be 21. 21 will be divided by 7 and multiplied by 6, which gives us a maximum score of 18, to allow a comparison between symptom and medication scores, since maximum scores for symptoms and medications are different in magnitude, as recommended by World Allergy Organization (WAO) guidelines. A combined symptom and medication score in accordance with WAO guidance on immunotherapy trials will then be calculated by dividing both scores by 6, summarize of the results and divide by 2. This will be performed by the AIT trial team and send on excel files to the Inform database. The mean composite score in each treatment group during the pollen season (beginning of May to end of July) and during the peak pollen season (approximately

mid-June, defined as the max 14 day rolling average pollen count during the season) will be compared.

2. Mini Rhinoconjunctivitis Quality-of-Life Questionnaire (miniRQLQ) scores will be collected weekly during the pollen season (Appendix 3 of protocol). The mean composite score in each treatment group during the peak pollen season (beginning of May to end of July) will be compared. Furthermore the maximum RQLQ will be compared.
Mini RQLQ will also be recorded pre- and post-season. Adding the scores of the 14 questions to form a single score per measurement will form the score of the mini RQLQ. The Inform database team will perform this.
3. Symptoms and severity of symptoms after intake of the daily tablets will be recorded on a daily questionnaire (Appendix 9 of protocol), which the participants will fill out at home. The type of symptom (itchy mouth, swelling of the mouth or other) and the WAO Grade of the local symptoms will be calculated daily and active will be compared. The duration of the symptoms in days and the duration of symptoms in minutes will be specified, the AIT trial team according to the records assessed on the paper CRF on every visit will give this information.
4. Global Evaluation Score 3 (Visual Analogue Scale of overall Hayfever symptoms in the last week) (Appendix 4 of protocol) will be collected weekly during the pollen season. The mean composite score in each treatment group during the peak pollen season (beginning of May to end of July) will be compared. Furthermore the maximum Global Evaluation Score 3 will be compared between the placebo and the active treatment group.
5. The total nasal symptoms score (TNSS) measured at 0, 5, 15, 30 and 60 minutes (Early phase response (EPR)) following grass pollen nasal allergen challenge at baseline, at 6 and at 12 months (Appendix 6) will be assessed similar to the primary endpoint.

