6.4.7 Assessment of compliance with study medication

Participants will be asked to return used AIT (Grazax®) and AIT placebo blister packs and unused tablets at each study visit. Those participants with less than 75% compliance with study medication will be counselled. Use of rescue medications (section 6.4.8.1) will be assessed by medication score (Appendix 5). The participant will fill out a daily Medication Diary in which he/she will record the Tablet intake (Appendix 9).

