6.4.8 Concomitant medication

6.4.8.1 Permitted Medications

The following rescue medications will be provided. These medications are considered standard of care and will be provided approximately 2 weeks before the start of the pollen season (May 2014) and throughout the pollen season:

- Antihistamine (e.g. desloratidine).
- Nasal corticosteroid (e.g. fluticasone propionate aqueous nasal spray).
- Ophthalmic antihistamine (e.g. olopatadine eye drops).

Use of the following rescue medications will be provided by the study only after participants are evaluated by the investigator. Evaluations may occur by phone contact or clinic visit.

- Oral corticosteroid (e.g. prednisolone).
- Short-acting beta-agonists (e.g. salbuterol).
- Inhaled corticosteroids (e.g. fluticasone).
- Combination long-acting beta-agonists or steroids (e.g. salmeterol/fluticasone).

Refer to **Appendix 7** for required medication washout periods prior to screening, nasal challenges and biopsies (V-1, V0b, V5, and V7).

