Appendix 5: Symptom and Medication Score

Please complete weekly on Wednesday during the pollen season from beginning of May until the end of July.

Symptom Score:

“How do you assess the severity of your hay fever symptoms when they were at their most severe during the last week (tick each single symptom)?”

Rhinoconjunctivitis / Hayfever Symptom		Symptoms			
		0 (None)	1 (Mild)	2 (Moderate)	3 (Severe)
Nasal Symptoms					
1	Runny nose				
2	Blocked nose				
3	Sneezing				
4	Itchy nose				
Eye Symptoms					
1	Itchy eyes				
2	Watery eyes				

Medication score:

“On how many days did you require use of rescue medications in the last week (tick each single medication)?”

Rescue medication	Number of days used			
	0 days	1-2 days	3-4 days	5 or more days
Antihistamine tablets				
Nasal spray				
Eyedrops				

Symptom and Medication Score (SMS) = (Symptom score/6 + Medication score/6)/2

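### The rescue-medication score in SAP 7.3.1 item 1 needs drug use day by day, but the Appendix 5 form it draws on records only banded day counts for three drugs and has no oral-corticosteroid row

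*SAP*

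**What the plan says.** **The score.** SAP 7.3.1 item 1 names Protocol Appendix 5 as the weekly self-assessment and says "Medication use will be recorded in weekly questionnaires by participants and a medication score will be calculated". Antihistamine tablet and/or eye drops earn 1 point per day, nasal spray 2 and oral corticosteroid 3. The SAP continues: "The maximum daily medication score will therefore be 3. The maximum weekly score will be 21". The weekly score is rescaled to a maximum of 18, to match the symptom score. Each score is then divided by 6, and the two are added and halved.

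Participants start with antihistamines and, "if this does not suffice adding treatment with nasal spray"; oral corticosteroid follows after contact with the trial team. On the calculation, the SAP says: "This will be performed by the AIT trial team and send on excel files to the Inform database".

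**The form.** The medication part of Appendix 5 asks: "On how many days did you require use of rescue medications in the last week". There are three rows (antihistamine tablets, nasal spray, eye drops) and four bands (0, 1-2, 3-4, 5 or more days). No points are printed against the bands. The formula is "Symptom and Medication Score (SMS) = (Symptom score/6 + Medication score/6)/2".

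**Other sources.** Protocol 6.4.7 relies on the Appendix 5 score for the rescue drugs of 6.4.8.1. That list includes oral corticosteroid, in a group introduced by "Use of the following rescue medications will be provided by the study only after participants are evaluated by the investigator". Concomitant medication is in the SAP 10.2.1 schedule, and SAP 9.1 uses medication start and stop dates from the CRF. Neither document links those dates to this score.

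**The concern.** The stated rule and the named data source do not fit together. A points-per-day score needs the drugs used on each day. The form gives a coarse weekly count per drug, with no way to see which drugs fell on the same day and nowhere to enter the drug that earns 3 points. The SAP gives no conversion, so two analysts could derive different medication scores from the same forms.

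The score is exploratory (Protocol 6.2.2, SAP 7.3.1). It still bears on a stated clinical hypothesis, reduction in seasonal symptoms and medication use (Protocol 5.3). Protocol 6.8.3.2 item 1 also compares the composite between arms at the 0.05 level.

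A related problem affects the weekly scores in the same SAP section: the word peak has three meanings, set out at the end of the working.

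**Working it through.** **1. The plan's own maxima.** 3 × 7 = 21 per week; 21/7 × 6 = 18; composite maximum (18/6 + 18/6)/2 = 3. These reproduce. One weekly medication point is therefore worth (6/7)/6/2 = 1/14 of a composite unit.

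**2. Which daily rule fits a maximum of 3?**
- Highest step used that day: maximum 3. Fits.
- Sum capped at 3: maximum 3. Fits.
- Plain sum: 1 + 2 + 3 = 6 per day, 42 per week, 36 rescaled. Does not fit.

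The two surviving rules differ on a day with antihistamine plus spray: 2 points against 3, or 14 against 21 over a full week.

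**3. What the form determines.** Assume no oral-corticosteroid use. Each of 7 days takes one of 8 combinations of tablet, spray and eye drops. I enumerated every allocation, grouped them by the 4 × 4 × 4 = 64 band patterns, and found the lowest and highest weekly score compatible with each pattern.

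| | Highest step | Capped sum |
|---|---|---|
| Patterns with a unique score | 1 of 64 (no use) | 1 of 64 (no use) |
| Median width, weekly points | 4 | 4 |
| Maximum width | 6 | 8 |
| Highest score from the form alone | 14 (12 rescaled) | 21 (18 rescaled) |

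If every spray day is also an antihistamine day (an assumption, suggested by the stepwise instruction), 54 patterns remain and still only 1 is unique. Median width is then 3 (highest step) or 4 (capped sum), and maximum width 5 or 6.

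**4. Two patterns by hand (no eye drops).** T = tablet days, N = spray days.
- *Both 3-4 days, highest step.* Minimum: T = N = 3 on the same days, 3 × 2 = 6. Maximum: T = N = 4 with one shared day, 4 × 2 + 3 × 1 = 11. Range 6-11, or 6-8 if spray days are antihistamine days.
- *Both 3-4 days, capped sum.* 2N + T runs from 9 to 12.
- *Both 5 or more days.* Highest step: 2 × 5 = 10 to 2 × 7 = 14. Capped sum: 15 to 21. On the composite: 10/14 = 0.71 to 14/14 = 1.0, against 15/14 = 1.07 to 21/14 = 1.5. The ranges do not overlap, so choosing a band mapping does not remove the need to state the daily rule.

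**5. Oral corticosteroid.** Take 3 such days from the CRF, scored 3 each, in a week with tablets and spray both at 3-4 days. Under highest step the score runs from 9 + 0 = 9 (all form use falls on those days) to 9 + 4 × 2 = 17. CRF dates supply the missing step but do not resolve the overlap.

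**6. Scoring the bands directly.** If the bands were scored 0 to 3 (an assumption; Appendix 5 prints no points), the medication maximum would be 3 × 3 = 9 and the composite maximum (18/6 + 9/6)/2 = 2.25, against 18 and 3 in the SAP. A band-based score therefore needs its own rescaling.

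**7. Season definitions, side by side.**
- SAP 7.3.1 item 1: start of May to end of July is the pollen season; the peak is the maximum 14-day rolling-average count. Protocol 6.8.3.2 item 1 gives the same peak.
- SAP 7.3.1 items 2 and 4: the same May-to-July dates are called the peak season.
- Protocol 6.5.5 and SAP 7.1.1: the peak starts and ends on runs of three days above and below 30 grains, and SAP 7.1.1 builds its peak variable from this.

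**The case against.** **The score is exploratory and the widths overstate the harm.** Largely right. Almost any banded form leaves most patterns without a unique score. The enumeration weights all patterns equally, without knowing how often each occurs, and each width is a worst case for one participant-week. A reader might take 4/14 = 0.29 as the error in the endpoint, or infer bias towards one arm. The documents support neither. The endpoint is a group mean over many weekly forms, and one mapping applied blind treats both arms alike.

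**The intended daily rule is clear enough.** This stands in part. The SAP lists steps of 1, 2 and 3 and concludes that the maximum is therefore 3, which follows directly from highest-step scoring. It mentions no cap, and a capped sum would score antihistamine plus spray the same as oral corticosteroid. It would go too far to present the two rules as equally supported. But participants are told to add spray to antihistamines, so the day on which the rules differ is the expected second step, and the SAP should say which applies.

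**Oral-corticosteroid use is recorded elsewhere.** It should be: access is through the investigator and the CRF holds start and stop dates. A reader might infer that this information is lost. What is missing is the link from those dates to the score.

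**A rule may exist in a trial SOP.** Possibly; SAP section 4 cites one for unblinding. The documents show that the SAP states no conversion, not that none was written.

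**The rolling-average peak is not a SAP slip.** Correct. It comes from Protocol 6.8.3.2, so that conflict already exists within the protocol. Calling all of May to July the peak appears only in SAP items 2 and 4.

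**Conclusion.** The point holds. As written, the medication half of this score cannot be computed from the form named as its source. Same-day use and the oral-corticosteroid step are absent, day counts are banded, and the daily rule is implied at most. Assuming no oral-corticosteroid use, 63 of 64 form patterns leave the weekly score open, and under highest step the form reaches at most 14 of 21.

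The cost is to precision and reproducibility. No bias between arms has been shown, and none is expected from a single mapping applied blind. The symptom half (0 to 18) can be computed, and the primary endpoint is untouched. This should be corrected, but it does not threaten the trial's main conclusion.

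**What to change.** Before unblinding:

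1. State the daily rule. Highest step appears intended.
2. If the form can still be changed, record the number of days (0 to 7) at each step. Otherwise prespecify one scoring of the collected bands with one overlap convention, restate the attainable maximum and the rescaling to match, and report one sensitivity analysis with the lowest and highest compatible scores. Check the mapping for feasibility. For example, midpoints under a capped sum give 2 × 3.5 + 1.5 = 8.5 for spray 3-4 days with tablets and eye drops 1-2 days each. If spray days must be antihistamine days, the lowest possible score there is 2 × 3 + 3 = 9.
3. Name the CRF concomitant-medication start and stop dates as the source of oral-corticosteroid days, and let the overlap convention cover weeks that contain them.
4. Separately, use one peak definition for all weekly scores. Relabel May to July in items 2 and 4 as the pollen season, and reconcile the 14-day rolling-average peak (SAP 7.3.1 item 1, Protocol 6.8.3.2) with the 30-grain peak (Protocol 6.5.5, SAP 7.1.1).

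The cost is a few lines of SAP text and, if still possible, a small form change. No visits or participants are added. If the banded form stays, some precision in the medication score is lost.
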